7.5 Leeds Dactylitis Index (LDI) Analysis Set

The leeds dactylitis index analysis set will consist of all the randomized subjects with non-zero LDI at baseline. Subjects will be analyzed according to their randomized treatment group. Analyses of LDI efficacy endpoints will be based on the leeds dactylitis index analysis set.

7.6 Modified Nail Psoriasis Severity Index (mNAPSI) Analysis Set

The mNAPSI analysis set will consist of all the randomized subjects with non-zero mNAPSI at baseline. Subjects will be analyzed according to their randomized treatment group. Analyses of mNAPSI efficacy endpoints will be based on this analysis set.

7.7 SPARCC Enthesitis Analysis Set

The SPARCC Enthesitis Analysis Set will consist of the randomized subjects with non-zero SPARCC enthesitis at baseline. Subjects will be analyzed according to their randomized treatment group. Analyses of SPARCC efficacy endpoints will be based on the SPARCC Enthesitis analysis set.

7.8 Subgroup Analysis

Subgroup analyses based on age (≤ 65 , > 65), sex (male, female), race (Caucasian, non-Caucasian), ethnicity (Hispanic or Latino, non-Hispanic or Latino), baseline BMI (≤ 30 , > 30), baseline weight (≤ 100 kg, > 100 kg), baseline BSA ($< 3\%$, $\geq 3\%$, $\geq 3\%$ and $< 10\%$, $\geq 10\%$), prior use of non-biologic DMARD (yes, no), and disease duration (\leq median, $>$ median, median is based on all randomized subjects.) will be performed for the primary and key secondary endpoints to examine any differences in drug responses. Also subgroup analyses based on baseline BSA ($< 3\%$, $\geq 3\%$ but $< 10\%$, and $\geq 10\%$) will be performed for sPGA and BSA in exploratory analysis.

Subgroup analysis containing a subgroup of less than 5% of the whole study population will not be conducted.

8. Interim Analysis and Early Stopping Guidelines

No interim analysis is planned for this study.

9. Data Screening and Acceptance

9.1 General Principles

The objective of the data screening is to assess the quantity, quality and statistical characteristics of the data relative to the requirements of the planned analyses.

9.2 Data Handling and Electronic Transfer of Data

Amgen's Clinical Data Management department will provide all data to be used in the planned analyses. This study will use the RAVE database for all data except patient reported outcomes (PROs) and tender and swollen joint counts, which will be collected electronically on a tablet, and radiographic and laboratory data. All PROs, tender and swollen joint counts, radiographic data, and laboratory data will be transferred to Amgen's Clinical Data Management and stored outside the RAVE database as described in the Data Management Plan and Data Transfer Plan.

9.3 Handling of Missing and Incomplete Data

Subjects may be missing specific data points for a variety of reasons. In general, data may be missing due to a subject's early withdrawal from study, a missed visit, or inability to evaluate an endpoint at a particular point in time. The general procedures outlined below describe what will be done when a data point is missing.

9.3.1 Missing Baseline Evaluation

Missing baseline evaluations will not be imputed.

9.3.2 Missing Post-baseline Evaluation

Subjects with missing post-baseline efficacy data will be imputed as non-responder, ie, non-responder imputation (NRI) for the primary analysis of primary and key secondary efficacy endpoints (ACR 20 and MDA). Data will also be analyzed using multiple imputation (MI) as sensitivity analyses for primary and key secondary endpoints (ACR20 and MDA).

For analyses of other efficacy endpoints after week 24, data from subjects who remain in the double-blind period will be analyzed as observed with no imputation for missing data. Data from subjects who enter open-label rescue therapy will be imputed using last observation carried forward (LOCF).

For non-radiograph exploratory endpoints, data will be analyzed as observed without imputation for missing data.

For radiographic exploratory endpoints, data will be analyzed as observed with no imputation for missing data or for subjects who enter rescue treatment. In addition, data will be analyzed using LOCF imputation for missing radiographs and for subjects who enter rescue treatment as sensitivity analysis.

Baseline data will not be carried forward to any missing post-baseline value unless otherwise specified.

Missing post-baseline safety data will not be imputed.

9.3.3 Missing Components of Composite Endpoints

The rules for handling missing individual joints and missing components of composite endpoints are described in [Appendix A](#).

9.3.4 Missing and Incomplete Dates

For any listings, missing or incomplete dates will be listed as is. No imputation will be done on incomplete stop date of an adverse event unless specified otherwise.

For tables, in the case where the start or stop date of an adverse event or concomitant medication is missing or incomplete, the following rule will be applied:

| | Missing | Imputation | Exception |
|--|---------------------|---------------|---|
| Start date (AE, concomitant medication) | Day | 01 | Default to Study Day 1 if an event starts the same year and month as Study Day 1 and Stop date is after Study Day 1 |
| | Day/Month, or Month | 01JAN | Default to Study Day 1 if an event started the same year as Day1 and Stop date is after Study Day 1 |
| | Day/Month/Year | No imputation | |

If the imputed start date is after the end date of concomitant medication or AE, then imputed start date will be default to end date of concomitant medication or AE.

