6.4 Study Time Intervals

Double-blind Treatment Period

The period of time beginning when a subject receives their first dose of IP through the first dose of rescue treatment, or end of study if they are never rescued. In case where a

subject is randomized but never dosed, the double blind period will start on the randomization date.

Rescue Therapy Period

The period of time between the first dose of open-label rescue therapy at or after week 24 through end of study.

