10.6.1 Adverse Events

The Medical Dictionary for Regulatory Activities (MedDRA) version 18.0 or later will be used to code all adverse events (AE) to a system organ class and a preferred term. All adverse event tables will be summarized by treatment group for the double-blind treatment period and the rescue therapy period. The subject incidence of AEs will be

summarized for all treatment-emergent AEs, serious AEs, AEs leading to withdrawal of investigational product, and fatal AEs.

Subject incidence of all treatment-emergent AEs, serious AEs, AEs leading to withdrawal of investigational product, and fatal AEs will be tabulated by system organ class and preferred term in descending order of frequency.

Summaries of treatment-emergent and serious AEs occurring in at least 1% of the subjects by preferred term in any treatment arm will be provided in descending order of frequency.

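### The SAP's rule for partial adverse event start dates has no exception for the first rescue dose, so rescue-period events whose reported month or year matches that dose are dated into the double-blind period

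*SAP*

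**What the plan says.** **Imputation (SAP 9.3.4, for tables).** The row for a missing day reads "Start date (AE, concomitant medication) | Day | 01", and the row for a missing month reads "Day/Month, or Month | 01JAN". A wholly missing date is not imputed. Each of the two rules has one exception. For a missing day it is "Default to Study Day 1 if an event starts the same year and month as Study Day 1", provided the stop date falls after Study Day 1. For a missing month it is "Default to Study Day 1 if an event started the same year as Day1 and Stop date is after Study Day 1". One further adjustment applies when the imputed start falls after the end date: "then imputed start date will be default to end date of concomitant medication or AE". None of these rules mentions the first rescue dose.

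**Periods (SAP 6.4).** The double-blind period is "The period of time beginning when a subject receives their first dose of IP through the first dose of rescue treatment", or through end of study if there is no rescue. The rescue period is "The period of time between the first dose of open-label rescue therapy at or after week 24 through end of study".

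**Use of the periods.** SAP 10.6.1 states: "All adverse event tables will be summarized by treatment group for the double-blind treatment period and the rescue therapy period". SAP 10.6 summarises rescue events separately so that they are shown against the treatment taken during rescue. SAP 6.1 labels that treatment etanercept plus methotrexate for every rescued subject. Under Protocol 3.1.2, combination-arm subjects with an inadequate response stay on the same treatment.

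**The concern.** The safety tables have two boundaries, Study Day 1 and the first rescue dose. The imputation rule protects the first from dates pulled too early and leaves the second unprotected.

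For a subject randomised to monotherapy, the treatment changes at rescue. An event that began on the combination but is dated back before rescue is reported under etanercept alone or methotrexate alone, and is missing from the rescue summary. That defeats the purpose SAP 10.6 gives for the separate summary. Events soon after the switch are the most exposed, and that is when the added drug is new and, under Protocol 7.2.5, methotrexate is being titrated.

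**Working it through.** The documents give no figure for this point, so there is none to reproduce. The check applies the SAP 9.3.4 rule to every possible date.

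**Direction.** An imputed start is either no later than the true onset or equal to Study Day 1, which precedes rescue. The end-date adjustment only moves a start earlier. An event can therefore cross from rescue to double-blind, but not the reverse.

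**Which events cross.** Day missing: those in the same calendar month as the first rescue dose, unless that dose is on the 1st. Month missing: those in the same calendar year, unless that dose is on 01JAN.

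**Assumptions (not in the documents).** Entry is uniform over the calendar and onset uniform from the day after the first rescue dose to week 48. The stop date is after both Study Day 1 and the imputed start. The period is assigned by imputed start date, with the first rescue dose date counted as rescue.

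**Rescue at week 24 (168 days of rescue follow-up).**

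- Day missing. In a month of L days, the mean number of later days in the same month, with rescue on the 1st contributing none, is (L − 1)(L − 2)/(2L). With L = 30.44 this is 29.44 × 28.44 / 60.88 = 13.75 days, and 13.75/168 = 8.2%.
- Month missing. For rescue on day d of a 365-day year, min(168, 365 − d) days cross, and none if d = 1. The sum is 196 × 168 + (167 × 168)/2 = 32,928 + 14,028 = 46,956. Dividing by 365 × 168 = 61,320 gives 76.6%.

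A day-by-day count over a four-year calendar cycle gives the same two values and extends them to later rescue:

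| First rescue dose | Day missing: moved | Month missing: moved |
|---|---|---|
| Week 24 | 8.2% | 76.6% |
| Week 28 | 9.8% | 80.4% |
| Week 36 | 16.4% | 88.1% |
| Week 44 | 49.1% | 95.8% |

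For onsets in the first 4 weeks of rescue the shares are 49.1% and 95.8%. With rescue at week 24, 30.9% of month-missing rescue events go all the way back to Study Day 1.

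**Example.** Study Day 1 is 10 Mar 2016 and the first rescue dose is 168 days later, on 25 Aug 2016.

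- True onset 28 Aug, day missing: imputed 01 Aug, so double-blind.
- True onset 14 Oct, day missing: imputed 01 Oct, so still rescue.
- True onset 14 Oct, only the year known: imputed 10 Mar, so double-blind.
- True onset 20 Jan 2017: imputed 01 Jan 2017 under either rule, so still rescue.

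**Effect of an added rescue exception.** If every matching event were moved to the first rescue dose, the error would reverse. With rescue at week 24, up to 8.8% of day-missing and 76.9% of month-missing events that truly began in the double-blind period would move into rescue. A stop-date condition limits this. In a simulation with uniform onset over 48 weeks, exponential durations averaging 5 to 30 days and rescue at week 24, misassignment in either direction, as a share of all partly dated events, fell from 4.4% to 1.2–3.2% (day missing) and from 38% to 1.4–8% (month missing). The gain shrinks as events last longer, and there is none for events that never resolve. For long-lasting year-only events with later rescue it can disappear.

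**The case against.** **The mechanism is inferred.** The SAP does not say that the imputed date assigns an event to a period. SAP 6.6 determines treatment emergence from a pre-treatment flag and the start date. SAP 6.1 identifies rescue from the drug administration forms. The Appendix B code is redacted. This stands as a limit on certainty. Even so, SAP 6.4 defines both periods by dose date, and no readable rule or flag places a partly dated event in rescue by another route.

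**Year-only onsets should be rare.** Protocol 9.2.1 requires onset dates, Table 1 schedules adverse event review at each treatment visit and at the visit 4 to 5 weeks after rescue starts, and Protocol 12.3 provides for data queries. The 77% is a share of a group that may be very small. This stands.

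**Placing an undatable event is partly a convention.** The present rule keeps it with the randomised treatment, and a simple rescue default would move genuine double-blind events out. For year-only dates the two exceptions would also compete whenever Study Day 1 and rescue fall in one calendar year: with rescue at week 24, (365 − 168)/365 = 54% of subjects. This stands against an unconditional default with no stated precedence. It does not justify sending every matching event one way when a known stop date can help to decide.

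**A stronger reading is tempting.** A reader might infer that partly dated rescue events in general are pushed into the blinded arms, or that the safety comparison is materially biased. The documents do not support either. With rescue at week 24, about 92% of day-missing rescue events stay in rescue, wholly missing dates are not imputed, and no count of partial dates is given.

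**Conclusion.** The gap is real but narrow. As written, SAP 9.3.4 dates a partly dated rescue-period event before rescue when its reported month (day missing) or year (month missing) is that of the first rescue dose, unless that dose fell on the 1st or on 01JAN. With rescue at week 24 and uniform onset, this is about 8% of day-missing and 77% of month-missing rescue-period events. The conclusion that such events enter the double-blind tables rests on assignment by imputed date, which is implied rather than stated.

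The consequence is minor. Only the monotherapy arms carry a wrong treatment label. The tables are descriptive (SAP 10.1 plans no formal safety testing), listings show partial dates as recorded, and no efficacy result is touched. It is worth correcting because the change is cheap and the present rule works against the SAP's own reason for separating rescue events.

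**What to change.** In SAP 9.3.4 and 10.6.1:

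1. State that adverse events are assigned to a period by imputed start date. State also that the day of the first rescue dose belongs to the rescue period, because the two definitions in SAP 6.4 meet on that day.
2. Add an exception: if the known part of the start date matches the month (or year) of the first rescue dose, and a known stop date is on or after that dose, set the start to the first rescue dose date. Give this precedence over the Study Day 1 exception.
3. For matching events that are ongoing or lack a complete stop date, keep the current imputation. Report their count by arm and tabulate them both ways.

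The cost is a few sentences in the SAP, a short piece of derivation code and a footnote or supplementary table. The downside is that some longer events that began before rescue will be counted in the rescue period. This is a date derivation only; it changes no dose and no rescue rule.

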9.4 Detection of Bias

The study has been designed to minimize potential bias by selecting subjects, allocating treatment groups, assessing endpoints, and handling withdrawals without knowledge of the treatment. Other factors that may introduce bias include:

- Important protocol deviations likely to impact the analysis or interpretation of results
- Blind breaking before database lock and formal unblinding
- IP dosing non-compliance
- Reasons for early withdrawal from treatment or from study

The incidence of these factors will be assessed. Important protocol deviations likely to impact the analysis and interpretation of results will be listed and/or tabulated in the Clinical Study Report (CSR). If a significant number of major protocol deviations are observed, an additional sensitivity analysis may be performed on the efficacy data excluding subjects with major protocol deviations.

Any breaking of the blind for individual subjects prior to formal unblinding of the study will be documented in the CSR, including the timing and reason for unblinding. The impact of such unblinding on the results will be assessed.

Tabulations of important protocol deviations (IPDs) related to IP dosing non-compliance by treatment group will be provided. A sensitivity analysis including subjects who tolerated at least 15 mg weekly of methotrexate (or placebo for methotrexate) after the initial 4-week titration through week 24 will be performed to assess the potential bias of methotrexate intolerance, as previously described in [Section 7.4](#).

Reasons for early withdrawals from treatment and from study will be summarized. If a significant pattern is observed, additional sensitivity analyses may be performed on efficacy data adjusting for reasons for early withdrawal.

9.5 Outliers

Descriptive summaries will be examined to identify unexpected values.

Outliers due to data entry errors will be corrected by the study team before data lock. Outliers that are not due to data entry will be included in the analysis. If it is deemed necessary after the team reviews the output from the planned analyses after data lock, a post-hoc sensitivity analysis excluding subjects with outliers may be performed.

9.6 Distributional Characteristics

All continuous endpoints that will be analyzed with an ANCOVA model will be evaluated with regards to their distributional characteristics. If they deviate from normality, data will be first transformed to their joint ranks and then further transformed by the van der Waerden method to normalize them before applying the ANCOVA model.

9.7 Validation of Statistical Analyses

Programs will be developed and maintained, and output will be verified in accordance with current risk-based quality control procedures.

Tables, figures and listings will be produced with validated standard macro programs where standard macros can produce the specified outputs.

The production environment for statistical analyses consists of Amgen-supported versions of statistical analysis software, for example the SAS System version 9.2 or later.

10. Statistical Methods of Analysis

10.1 General Principles

The primary analysis will be performed after all subjects have completed the week 48 assessments and the 30-day safety follow-up period and all data have been finalized.

Subject disposition, demographics, and baseline disease characteristics will be summarized descriptively by randomized treatment group.

For categorical endpoints, the descriptive statistics will contain the frequency and percentage. For continuous endpoints, the descriptive statistics will include the number of observations, mean, standard error, standard deviation, median, minimum, and maximum.

Treatment effect will be tested for the primary and key secondary endpoints using a Bonferroni-based gatekeeping chain procedure to control the family-wise 2-sided type one error rate at 0.05. The significance level for the analyses of other secondary endpoints and exploratory endpoints will be 0.05 without adjusting for multiplicity and the p-values for these endpoints will therefore be treated as a descriptive statistic only. Safety endpoints will be tabulated by actual treatment received during the study. No formal statistical testing will be performed for safety analyses.

10.2 Subject Accountability

Subject disposition will be summarized descriptively for all randomized subjects by randomized treatment group.

The disposition for the double-blind treatment period will include the number of subjects who are randomized, who are dosed with investigational product, who complete 24 weeks, who complete 48 weeks, who complete the study, and who withdraw prematurely including their reasons for withdrawal.

The disposition for the rescue therapy subjects will include the number of subjects who enter rescue therapy, who complete 48 weeks, who complete the study, and who withdraw prematurely including their reasons for withdrawal.

10.3 Important Protocol Deviations

Important Protocol Deviations (IPDs) categories are defined by the study team before the first subject's visit and updated during the IPD reviews throughout the study prior to database lock. These definitions of IPD categories, sub-category codes and descriptions will be used during the course of the study.

10.4 Demographic and Baseline Characteristics

Subject demographic and baseline disease characteristics will be summarized descriptively for all randomized subjects by randomized treatment group. Demographic and baseline disease characteristics may be re-evaluated for the safety evaluable subset if the subset is materially different from the full analysis set.

In addition, subject demographic and baseline disease characteristics will be summarized descriptively for all subjects who receive rescue therapy by randomized treatment group.

10.5 Efficacy Analyses

All efficacy analyses of non-psoriasis efficacy endpoints will be conducted using the full analysis set (ie, intent-to-treat set). Analyses of psoriasis efficacy endpoints (eg, sPGA, BSA) will be based on the psoriasis efficacy analysis set and other subgroups using different cutoffs of baseline BSA. Some PsA efficacy endpoints will be analyzed using analysis sets corresponding to those PsA indications. Subjects will be analyzed according to their original randomized treatment regardless of the actual treatment received during the study.

For the primary and key secondary endpoints, missing post-baseline data will be imputed using non-responder imputation (NRI) for the primary analysis. In addition, the primary and key secondary endpoints will be analyzed using multiple imputation (MI) as a sensitivity analysis. Another sensitivity analysis for primary and key secondary endpoints will also be performed using Adequate Methotrexate Analysis Set. For analyses of other efficacy endpoints after week 24, data from subjects who remain in the double-blind period will be analyzed as observed with no imputation for missing data. Data from subjects who enter rescue period will be imputed using LOCF.

[figure not shown]
10.5.1 Analyses of Primary and Key Secondary Efficacy Endpoints

The primary analysis of the primary and key secondary endpoints, ACR 20 response and MDA response at week 24, will be performed using the full analysis set. Missing post-baseline data will be imputed using non-responder imputation (NRI) for the primary analysis. Treatment effect will be tested using the stratified Cochran-Mantel-Haenszel (CMH) test with baseline BMI and prior non-biologic DMARD use as the stratification factors.

[figure not shown]
To control the family-wise 2-sided type one error rate at 0.05 for the multiple comparisons of the etanercept plus methotrexate therapy and etanercept monotherapy groups with methotrexate monotherapy across the primary and key secondary endpoints, the hypotheses will be tested using a Bonferroni-based gatekeeping chain procedure ([Burman et al 2009](#) and [Millen et al 2011](#)) as shown in [Figure 1](#). This procedure will split alpha of 0.05 equally to test in parallel the primary and key secondary endpoints (ACR 20, MDA) for etanercept plus methotrexate therapy vs. methotrexate monotherapy and etanercept monotherapy vs. methotrexate monotherapy sequentially

within each parallel path. If one of the parallel paths rejects both hypotheses sequentially, and the other parallel path has at least one hypothesis not rejected, then the unspent alpha of 0.025 from the successful path will be propagated to the hypotheses in the other path to re-test them sequentially at a level of 0.05. For example, suppose the nominal p-values for hypotheses A1, B1, A2, and B2 (Figure 1) are 0.01, 0.02, 0.03, and 0.055, respectively. In the first round of testing, hypotheses A1 and B1 are rejected, whereas hypotheses A2 and B2 are not rejected. However, since both hypotheses A1 and B1 are rejected, the procedure gives a second chance to re-test hypotheses A2 and B2 (according to the left arm of the figure) at a lower threshold of 0.05 rather than the original threshold of 0.025. Note that in this example A2 is rejected and hypothesis B2 is not rejected.

Figure 1. Bonferroni-based Gatekeeping Chain Procedure

ETN: Etanercept; MTX: Methotrexate

In addition, the primary and key secondary endpoints will be analyzed using multiple imputation (MI) as a sensitivity analysis. Another sensitivity analysis for primary and key secondary endpoints will also be performed using Adequate Methotrexate Analysis Set. Sensitivity analyses of primary and key secondary endpoints are descriptively without adjusting for multiplicity.

